## 10.1.2 Subject Identification Number

Upon signature of the ICF, each subject will be assigned a Subject Identification Number.

This Subject Identification Number will be allocated in ascending sequential order to each subject. For the duration of the entire clinical trial, the subject will be identified using the Subject Identification Number for all documentation and discussion.

## 10.1.3 Method of treatment assignment

Prior to the start of the trial, a randomization list will be generated by a statistician from CPCAD and will be transmitted to the person in charge of the products application.

Clinical Trial Protocol MC2-01-C4

The list will indicate the assignment of the seven products to the seven different test sites (1-7) of each Subject, according to a Latin squares design. The order of applications will be 1 to 7 for all Subjects.

# 10.1.4 Randomization number

At Day 1, each Subject who fulfils all inclusion/non-inclusion criteria will be assigned a Randomization Number. This three-digit Randomization Number will be dispensed in the chronological order of his/her inclusion in the trial and no number should be omitted or skipped. The date and time of randomization define this number, independently of the Subject Identification Number that was initially assigned at the Screening visit.

# 10.1.5 Instructions for use and administration

All applications will be performed at the trial center by a person from the investigational team other than the two independent trained readers. Application will be supervised by a second person also other than the two independent trained readers.

All trial drugs will be accounted for and in no case used in any unauthorized situation. All used and unused trial drugs will be appropriately inventoried and disposed of by the trial center.

# 10.1.6 Location of test sites

Seven circular sites (2.2 cm diameter) will be outlined on the anterior surface of the forearms. A number will identify them: 1 to 4 on one arm and 5 to 7 on the other arm (from the antecubital fossa to the wrist). The test sites will be delimited using a disposable circular device.

The distal part of the wrist, the veins, and hair covered areas should be avoided. Test sites should be no closer than 3 cm to the antecubital fossa or to the wrist. The distance between two test sites must be at least 2.5 cm center to center (i.e. at least 0.3 cm between site perimeters) and might be in straight line or staggered pattern, depending on the surface suitability (e.g., vascularity, nevi, etc.) and arm length.

As assessment will be visual no untreated control site is required.

# 10.1.7 Application procedure

The seven tested products will be randomly allocated to 7 sites. The 7 test sites will be numbered from 1 to 7. The treatments will be applied at the investigational site center by a qualified person, using a marker pen to define the areas of products application. A transparent sheet will be used to landmark the test sites location on each forearm.

The person in charge of applications will use a calibrated Eppendorf system with appropriate combitips to dose  $20\mu$ L of the tested product. One system will be dedicated to one tested product. Before the study start, every system will be checked according to CPCAD SOP PT 013 06 2018 01 18 - Eppendorf multipette. The check form will be retained in the study file. The combitip is filled by removing the plunger, filling the combitip and putting the plunger in place before connecting the combitip to the Eppendorf multipette.

Clinical Trial Protocol MC2-01-C4

Final Approved Version 20/08/2018

The  $20\mu$ L of products will be applied to each test site and gently massaged into the skin using a gloved finger. Each product will be applied using a different gloved finger.

After application and rubbing in, the test sites will be protected by a non-occlusive device. At the end of the application period (16 hours after application), remaining topical product will be gently removed from the skin by 3 consecutive swabbings with dry paper tissue swabs (no washing).

# 10.1.8 Subject Treatment Instructions

At screening phase (visit 1) and Day 1 (visit 2), an instruction sheet will be handed out to the subject. The instructions will apply throughout the trial.

According to this the subject will be instructed that:

- No occlusive dressing is permitted
- The devices should remain in place during the treatment period (16 hours)
- Bathing (bathtub, lake/sea), swimming and sauna is not permitted during Day 1 and Day 2 before the clinical evaluation
- Washing and direct showers on the test sites (forearms) are not allowed during Day 1 and Day 2 before the clinical evaluation
- No excessive sun exposure, as well as any kind of sun exposure of test sites is allowed.
- No sun cream or oil application on the test sites during Days 1 and 2.
- Subjects will abstain from strenuous physical activity and alcohol intake during Day 1 and Day 2 before the clinical evaluation.

# 10.1.9 Trial drug(s) packaging and labelling

MC2-01 / MC2-01 vehicle will be dispensed in 60 g aluminum tubes. The labels will be printed in French. The text of the labels will detail the information requested by Good Manufacturing Practice and local regulations.

Clinical Trial Protocol MC2-01-C4

Final Approved Version 20/08/2018

Etude : MC2-01-C4 Eudract n°2018-001673-24 Pour recherche biomédicale uniquement Tube de 00g vvvvvv Code du traitement : 0 Date d'expiration: DD MMM YY Numéro de lot : NNNNNN A appliquer sur les zones de test selon le protocole Pour usage externe uniquement A conserver entre 00 et 00°C, ne pas congeler Nom de l'Investigateur: [name] Drug Delivery Solutions Ltd (DDS) c/o MC2 Therapeutics A/S [name] [name], Denmark, [contact] L0011

Figure 2- Model of label (in French)

Commercially available reference products will be used from their commercial packaging and packed in a uniform outer package, in order to blind the product.

The products will be coded A, B, C, D, E, F and G.

## **10.2** Supplies management

#### 10.2.1 Accountability

Upon receipt of the trial drug(s), the designee product manager will maintain accurate records of the trial drug(s) delivery to the clinical trial center, the inventory at the clinical trial center, the reconciliation of all trial drug(s) received from the Sponsor, and the return to the Sponsor or alternative disposal of used and unused trial drug(s).

The designee product manager is required to sign and return the original "Receipt of Clinical Supplies" Form (or any acknowledgment of receipt) upon receipt and inspection of the supplies, fax the signed copy to sponsor and retain a copy within the clinical trial file.

All used and unused clinical trial drug(s) will be appropriately inventoried by the monitor and returned to the Sponsor for destruction as instructed by the sponsor.

All clinical trial drug(s) sent to the Investigator/Institution will be accounted for and no unauthorized use is permitted.

Clinical Trial Protocol MC2-01-C4

# 10.2.2 Storage of clinical trial drug(s)

Trial drug(s) must be stored in a safe and secure area with restricted access, under the storage conditions specified by sponsor (see Table 2 - Description and usage of the investigational and reference products).

## 10.2.3 Dispensing and return

No drug will be dispensed directly to the subject. Trial drugs will be applied at the clinical center on Day 1. The person in charge of product applications will not be the Investigator/evaluator.

In the event of early termination/suspension of the clinical trial, a rapid recall of trial drug(s) will be initiated.

# 10.2.4 Treatment compliance management and record

Since product applications will be performed by a qualified person and verified by a second individual, who will not be the investigator/evaluator, treatment compliance will be ensured and documented appropriately by trial staff.

## 10.2.5 Dose modification

Not applicable

## 10.3 Blinding

## 10.3.1 Verification of blinding

The trial will be performed as an investigator-blinded trial since the following procedures will be followed in order to prevent the Investigator and/or other Evaluator(s) from coming into contact with the trial materials thereby compromising the blinding of the trial.

All applications will be performed by designated trial personnel at the trial site. The trained observers performing the clinical assessments must not perform the application of the investigational products. Likewise, the site personnel performing the applications will be the only persons at the site having access to the randomization schedule.

The packaging and labelling of the investigational products will allow to distinguish their identity.

The subjects may be able to distinguish between the various applied formulations. They will therefore be instructed not to reveal any information about the trial medications to the (sub)investigator and/or trained observers performing the clinical assessments.

The tubes will be labeled with a letter A, B, C, D, E, F or G by IMP Pharmaceutical Services. IMP Pharmaceutical Services will furthermore create a document, listing which reference product is A, B etc. CPCAD will receive a copy of this document, sealed in an envelope, to be used in case of emergency. Access to the identification of treatment codes will be limited to the designated personnel.

Clinical Trial Protocol MC2-01-C4

# 10.3.2 Unblinding during the clinical trial

Emergency unblinding during the clinical trial may be required for therapeutic or for regulatory reasons (for expedited safety reporting).

A blind break system will be available for the investigator. At the clinical center, a sealed document, containing the identification of tubes of trial medication, may be revealed in emergency situation only. This list will be compared with the sequence of applications done for the subject in question by the person in charge of the applications or a designated person different from the investigator/readers. The information will be transmitted to the investigator only for the subject involved and documented.

The Investigator must notify the Sponsor's Clinical Safety Responsible immediately in the event of such an emergency (see contact details in Section 11.2.2.2. The Investigator should notify the Sponsor before breaking the blind in order to discuss this decision with the Sponsor. The Investigator is required to document each case of emergency unblinding on the randomization disclosure form (provided by the Sponsor) and fax the completed form to the CSR immediately.

# **11 CLINICAL TRIAL ASSESSMENT**

# 11.1 Pharmacodynamic (Skin blanching) assessments

Throughout the trial, the assessment of the blanching response for each individual test site (mini test site) will be performed to the extent possible by the same 2 trained evaluators. In the event there is a change in the assigned readers for a given Subject, the reason for change must be documented. If it is not possible to use the same reader to follow a given Subject, the Sponsor recommends that evaluations between the primary and subsequent evaluator overlap (both evaluators should examine the Subject together and discuss findings) for at least one visit.

## 11.1.1 Visual Assessment of Skin Blanching

Visual assessment of blanching will be made independently by two trained readers on Day 2 (2 hours after removal of products, following 16 hours application time) according to the following scale:

Score*	Description
0	No change in color skin
1	Slight (barely visible) blanching
2	Obvious blanching
3	Intense blanching
4	Blanching judged to be maximal

Table 3 - Skin blanching visual scale

\*Intermediate scores (half units) may be used when needed (e.g. 0.5 for a doubtful blanching).

This document will be regarded as confidential and proprietary in nature and will not be disclosed to any third party without sponsors written consent

Clinical Trial Protocol MC2-01-C4

Final Approved Version 20/08/2018

Two visual score values (one per trained evaluator) will be recorded for each test site.

## 11.1.2 Assessment of Local Tolerability

At Day 2, the (sub)investigator will assess each test site for local tolerability according to the scale in Table 4.

Table 4 - Local tolerability scale

Score*	Description
0	No reaction
0.5	Only slight erythema
1	Only erythema
2	Erythema with papules or oedema
3	Erythema, oedema with papules, oedema with vesicle
4	Blisters
IR	Irritant reaction including: miliaria (sweet rash), follicular pustules, burn-like reactions, dry scales

Subjects with a local tolerability score >0 will be re-assessed at a follow-up visit.

Cutaneous reactions scored as local tolerability will be reported as local AEs.

## **11.2** Safety assessment

A safety assessment will be conducted for all subjects at the screening visit (from the Informed consent signature) and every subsequent visit. The safety parameters are AEs, to be recorded as specified in Section 11.2.2.1, global cutaneous tolerance assessments, physical examination and vital signs assessments (Screening visit only).

Adverse events will be reported individually on an ongoing basis.

All clinical medical events, whether observed by the Investigator or reported by the Subject will be considered adverse events and recorded on the appropriate Adverse Event form. Assessment of severity and causality will be based on specific definitions.

Clinical Trial Protocol MC2-01-C4

## 11.2.1 Systemic safety assessment

## 11.2.1.1 General Physical examination

The following body systems should be evaluated as "normal" or "abnormal" by the Investigator, at the screening visit: Skin, Lungs, Abdomen, Eyes/ears/nose/throat, Musculoskeletal system, Lymph nodes, Cardiovascular system.

The Investigator may choose to further investigate any other sign that he/she observes during the physical examination.

All abnormal findings at the screening visit identified as clinically significant by the Investigator, will be recorded in the Medical History form.

For any clinically significant changes from the screening visit, an AE is to be recorded.

## 11.2.1.2 Vital signs

Evaluation of vital signs will be performed after 5 minutes rest in the sitting position at the screening visit. It will include measurement of systolic and diastolic blood pressure and pulse rate in the supine position.

All abnormal values at the screening visit identified as clinically significant by the Investigator, will be recorded in the Medical History form.

For any clinically significant changes from the screening visit, an AE is to be recorded.

For AEs, whenever possible, the Investigator is to provide a diagnosis rather than to report individual laboratory abnormalities.

## 11.2.2 Adverse Events

Adverse events (AEs) are to be monitored throughout the course of the clinical trial. All AEs are to be reported on the Adverse Event Form of the CRF with complete information as required. If AEs occur, the main concern will be the safety of the subjects. At the time of the ICF signature, each subject must be provided with the name and phone number of clinical trial center personnel for reporting AEs and medical emergencies.

## 11.2.2.1 Definitions

#### Adverse events (AE)

According to ICH E2A, an AE is any untoward medical occurrence in a subject or clinical investigation subject administered a pharmaceutical product and which does not necessarily have a causal relationship with this treatment. An AE can therefore be any unfavourable and unintended sign,

Page 37/54

Clinical Trial Protocol MC2-01-C4

Final Approved Version 20/08/2018

symptom, or disease temporally associated with the use of a medicinal (investigational) product, whether or not related to the medicinal (investigational) product.

Thus, any new sign or symptom or disease, or any clinically significant worsening of an existing sign, symptom or disease compared to the condition at the first visit (including disease treated), should be considered as an AE. Lack of efficacy is not considered as an AE.

Each new episode of a chronic disease (e.g., hay fever, allergy, etc...) should be reported as a new AE.

Any new sign or symptom reported by the subject that appears after accidental or intentional overdose or misuse should also be reported as an AE.

There should be an attempt to report a diagnosis rather than the signs, symptoms associated with the report of an AE. However, a diagnosis should be reported only if, in the Investigator's judgment, it is relatively certain. Otherwise, symptoms or signs should be used to describe the AE.

#### Serious Adverse events (SAE)

An SAE is any untoward medical occurrence that at any dose:

- Results in death,
- Is life threatening,
- Requires inpatient hospitalization or prolongation of existing hospitalization,
- Results in persistent or significant disability/incapacity, or
- Is a congenital anomaly/birth defect.

Important medical events that may not result in death, be life-threatening, or require hospitalization may be considered an SAE when, based upon appropriate medical judgment, they may jeopardize the safety of the subject, and may require medical or surgical intervention to prevent one of the outcomes listed in this definition. Examples of such events are intensive treatment in an emergency room or at home for allergic bronchospasm, blood dyscrasia, or convulsions that do not result in hospitalization.

Note: The term "life threatening" refers to an event in which the subject was at risk of death at the time of the event; it does not refer to an event that hypothetically might have caused death if it was more severe.

Inpatient hospitalization is considered to have occurred if the subject has had to stay for a night at the hospital. The criterion for prolongation of hospitalization is also defined as an extra night at the hospital. Hospitalization may not constitute sufficient grounds to be considered as an SAE if it is solely for the purpose of a diagnostic tests (even if related to an AE), elective hospitalization for an intervention that was already planned before subject enrolment in the clinical trial, admission to a day care facility, social admission (e.g., if the subject has no place to sleep), or administrative admission (e.g., for a yearly examination).

#### Unexpected adverse drug reaction

According to ICH E6, an unexpected adverse drug reaction is defined as an adverse reaction, the nature or severity of which is not consistent with the applicable trial drug information (e.g., Investigator's

Page 38/54

Clinical Trial Protocol MC2-01-C4

Brochure for an unapproved investigational product or the package insert/summary of product characteristics for an approved product).

#### Adverse event reporting period

The clinical trial period during which AEs must be reported is the period from when the subject signed the Informed Consent Form to the end of the subject's participation.

The Sponsor should be informed if the Investigator becomes aware of any unusual safety information or any safety information that appears to be drug related involving a subject who has participated in a clinical trial, even after a subject has completed the clinical trial. The Investigator should be diligent in looking for possible latent safety effects that may not appear until a medication has been discontinued.

#### Severity

Severity is a clinical determination of the intensity of an AE and not of a disease.

The Investigator is to classify the intensity of AEs using the following definitions as a guideline for all AEs occurring during the conducted clinical trial. For this classification, the Investigator will take into account the possible range of the intensity of the event and report the grade of intensity which is the most appropriate according his medical judgment.

- Mild Awareness of signs or symptom, but easily tolerated.
- Moderate Discomfort, enough to cause interference with usual activity
- Severe Incapacitating with inability to work or perform usual activity

## Relationship to the trial drug(s)

The Investigator is to determine whether there is a reasonable causal relationship between the trial drug(s) and the AE. Medical judgment should be used to determine the relationship, considering all relevant factors including the pattern of reaction, temporal relationships, positive challenge or rechallenge, relevant medical history, and confounding factors such as co medication or concurrent diseases.

The expression "reasonable causal relationship" is meant to convey in general that there are facts or arguments to suggest a causal relationship (ICH E2A, Section IIIA 1).

The relationship assessment for an AE is to be completed using the following definitions as a guideline for all AEs occurring during clinical trials:

• Reasonable Possibility:

According to the reporting Investigator, there is a reasonable possibility (i.e., suggestive evidence or arguments) that there is a causal relationship irrespective of the dose administered between:

The trial drug (investigational product, active reference, or vehicle, etc.) and the AE,

The clinical trial protocol procedure (e.g. product application, etc.) and the AE.

• No Reasonable Possibility:

This document will be regarded as confidential and proprietary in nature and will not be disclosed to any third party without sponsors written consent

Page 39/54

Clinical Trial Protocol MC2-01-C4

Final Approved Version 20/08/2018

No suggestive evidence or arguments can be identified regarding a causal relationship between the trial drug or the clinical trial protocol procedure and the AE.

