## Product application

The products will be allocated to each test site according to a pre-determined randomization scheme. The specified dose of each product will be applied to the delimited area and gently massaged into the skin using a gloved finger. Each product will be applied using a different gloved finger.

The test sites will be protected by a plastic ring and covered with a non-occlusive gauze dressing to avoid any lateral spreading of the product from the application site.

At the end of the application period (16 hours after application), any remaining topical product will be gently removed from the skin by 3 consecutive swabbings with dry paper tissue swabs (no washing).

During the application phase, the temperature of the room will be kept constant at 22-24 °C.

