#### 11.2.2.2 Reporting procedures

#### **Procedures for reporting Adverse Events**

The collection of AEs is from the time that subjects signs the ICF to their final visit.

At each post enrolment visit, the Investigator (or sub-Investigator) will question the subject about AEs using an open non-persuasive question to elicit reporting of AEs, for example "Have you noticed any change in your health since the last visit?" Directed questioning and examination will then be performed as appropriate.

Any AE occurring during the AE reporting period, whether it is related to the trial drug(s) or not, will be recorded immediately in the source document, and described on the Adverse Event Form of the [CRF along with the date of onset, severity, relationship to the trial drug(s), and outcome, without omitting any requested and known information. Additional information may be requested under certain circumstances. Adverse Events (AEs) assessed as related to the treatment will be monitored until they are completely or satisfactorily resolved. Other AEs will be monitored until the last visit if they are not resolved or satisfactorily resolved.

The Investigator will obtain and maintain in the subject's files all pertinent medical records, information and medical judgment from colleagues who assisted in the treatment and follow up of the subject. If necessary, the Investigator will contact the subject's personal physician or hospital staff to obtain further details.

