#### 13.3.2 Adverse events

Adverse events will be coded during the course of the trial and will be in accordance with the current version of the MedDRA dictionary. The adverse events will be tabulated by Preferred Terms and System Organ Class.

The number of subjects experiencing each type of adverse event (according to MedDRA Preferred Terms and System Organ Class) will be tabulated regardless of the number of times each adverse event is reported by each subject.

Adverse events where the investigator has not excluded a causal relationship to trial medication (i.e. not described relationship as "no reasonable possibility", adverse drug reactions) will be evaluated separately. A table or a description of these ADRs will be produced depending on the number of ADRs. As with adverse events, the number of subjects affected, not the number of events, will be considered.

The causal relationship of adverse events to trial medication and the intensity of adverse drug reactions will be tabulated or described. Where there are several recordings of causal relationship and intensity for the same event, causal relationship will be taken from the last report of the event (since that is when the investigator will be in possession of most information and so best able to judge causal relationship) and intensity will be taken as the worst ever recording. Adverse events observed on the application areas will be tabulated or described by treatment.

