## 5.3.2 Adverse events (AEs)

An overview of all AEs occurred during the trial will be presented as follows:

	Safety Popu	ulation (N=XX)
	n events	n (%) subjects
All AEs		
Related AEs		
All cutaneous AEs		
Related cutaneous AEs		
All serious AEs		
Related serious AEs		
Severe AEs		
Related severe AEs		
AEs of special interest		
AEs leading to discontinuation		
Related AEs leading to discontinuation		
Deaths		

Adverse events will be coded during the course of the trial and will be in accordance with the current version of the MedDRA dictionary. The adverse events will be tabulated by Preferred Terms and System Organ Class.

The number of subjects experiencing each type of adverse event (according to MedDRA Preferred Terms and System Organ Class) will be tabulated regardless of the number of times each adverse event is reported by each subject.

Adverse events where the investigator has not excluded a causal relationship to trial medication (i.e. not described relationship as "no reasonable possibility", adverse drug reactions (ADR)) will be evaluated separately. A table or a description of these ADRs will be produced depending on the number of ADRs. As with adverse events, the number of subjects affected, not the number of events, will be considered.

The causal relationship of adverse events to trial medication and the intensity of adverse drug reactions will be tabulated or described. Where there are several recordings of causal relationship and intensity for the same event, causal relationship will be taken from the last report of the event (since that is when the investigator will be in possession of most information and so best able to judge causal relationship) and intensity will be taken as the worst ever recording. Adverse events observed on the application areas will be tabulated or described by treatment.

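### The causality scale rates an event caused only by a trial procedure as a reasonable possibility, and both documents then count it as an adverse drug reaction

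*Protocol*

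**What the plan says.** Protocol 11.2.2.1, under the heading on relationship to the trial drug(s), opens with a question about the drug: "The Investigator is to determine whether there is a reasonable causal relationship between the trial drug(s) and the AE". It then gives a two-level scale. *Reasonable Possibility* lists two links. One is "The trial drug (investigational product, active reference, or vehicle, etc.) and the AE"; the other is "The clinical trial protocol procedure (e.g. product application, etc.) and the AE". *No Reasonable Possibility* applies when there is no suggestive evidence of a "causal relationship between the trial drug or the clinical trial protocol procedure and the AE".

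Protocol 11.2.2.2 lists what goes on the adverse event form: "date of onset, severity, relationship to the trial drug(s), and outcome". No separate entry for procedure causality is described in either document.

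Protocol 13.3.2 and SAP 5.3.2 share one rule for adverse drug reactions. The set is introduced as "Adverse events where the investigator has not excluded a causal relationship to trial medication" and made operational as every event "not described relationship as 'no reasonable possibility', adverse drug reactions". The SAP overview table adds five related rows (all, cutaneous, serious, severe, and leading to discontinuation) and no row for procedure-related events.

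**The concern.** The scale answers a question about drug or procedure, while the analysis reads the answer as being about the drug alone. An investigator who is confident that a skin reaction came from a procedure has no entry that says so.

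The path is a realistic one in this trial. Under protocol 7.1.2 the sites are outlined with a marker pen, and "The test sites will be protected by a plastic ring and covered with a non-occlusive gauze dressing" for the 16-hour application, after which each site is dry-swabbed three times. Protocol 11.1.2 turns cutaneous reactions scored on the tolerability scale into local adverse events, and that scale includes a 0.5 grade for slight erythema and a separate irritant category. Such events therefore reach the causality question. Protocol 10.1.6 plans no untreated site, so no site shows what the procedures do without a product.

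At stake is the meaning of the adverse drug reaction count and the related-event counts in the safety report. Some of what they label as reactions to trial medication may be events that the investigator did not attribute to any product.

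**Working it through.** The plan states no figure on this point. The check is to follow one event through the written rules.

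**Inputs:** the scale (protocol 11.2.2.1), the form entry (protocol 11.2.2.2), the adverse drug reaction rule (protocol 13.3.2, SAP 5.3.2), and the overview table and by-treatment rule (SAP 5.3.2).

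| Investigator's view of cause | Category under the scale | Status in the analysis |
|---|---|---|
| Drug suspected | Reasonable Possibility, first link | Adverse drug reaction |
| Procedure only | Reasonable Possibility, second link | Adverse drug reaction |
| Neither | No Reasonable Possibility | Not an adverse drug reaction |

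The second line is the fault. The lower category is closed to a procedure-only event because it requires the procedure to be excluded as well. With two levels and one entry, only the upper category is left, and the analysis rule then relabels it as a link to trial medication.

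**Which outputs are touched.**

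1. *Adverse drug reaction table or description:* yes, by definition.
2. *Overview rows:* the SAP does not define the word related separately, so I take it to follow the same rule. Ordinary site reactions would then enter the rows for related events and related cutaneous events. They enter the related serious, severe or discontinuation rows only if they also meet those criteria.
3. *Application-area events by treatment:* the rule covers all such events whatever their causality rating. The scale does not create this attribution, and changing it would not remove it.
4. *Local tolerability scores (SAP 5.3.1):* tabulated by product without using causality, so unaffected.
5. *Comparisons between products:* all seven sites in a subject, the vehicle site included, go through the same procedures, so no product is favoured.

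**Scale of one event.** If all 36 randomized subjects are in the safety set, each subject whose only related event is procedural adds 1/36 = 2.8 percentage points to the related-event percentage. How many such subjects there would be cannot be derived from the documents.

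**The case against.** The strongest reply is that the text mostly points to a drug-only rating. The section heading, the opening question, the form entry and the phrase trial medication in the analysis sections all refer to the drug, and the scale is offered as a guideline subject to medical judgment. An investigator might well rate a ring or marker reaction as unrelated. This stands to the extent that misclassification is possible and not certain. It does not remove the problem: that rating contradicts the category's own wording, and two assessors could code the same event differently.

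A second reply is that over-counting related events in a descriptive summary hides no harm and drives no test. That is correct and limits the weight of the point. The counts would still not mean what their label says.

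A third is that the only procedure named in the scale is product application, which is hard to separate from the product. The ring, gauze, marker and swabbing are my examples. They are protocol procedures and fall under the open-ended wording, but the documents do not name them there.

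Some stronger readings are tempting and are not supported:

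- A reader might infer that a procedure-only event enters every related row, or that tolerability results for individual products are distorted. The trace above shows neither follows, and the overview table has a single safety-population column.
- A reader might infer that the two causes could never be separated afterwards. The adverse event form is not in the documents, and event descriptions may identify the cause in some cases.
- A reader might put a rate on it: 3% to 10% of 36 subjects gives 36 × 0.03 = 1.1 to 36 × 0.10 = 3.6, or about one to four subjects. Those rates are assumed, and nothing in either document supports them.

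**Conclusion.** The point holds in a limited form. As written, the rules count an event attributed only to a procedure as an adverse drug reaction, and the SAP repeats the protocol's rule without correcting it. The consequence is possible inflation of absolute adverse drug reaction counts, and mainly of two overview rows. The primary blanching analysis is untouched.

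This rests on three assumptions: that investigators apply the written categories, that the form carries the single relationship entry the protocol describes, and that the overview's related rows use the adverse drug reaction rule. If investigators answer about the drug alone, the counts would be right, but the scale would still need rewording to match that practice. It is worth correcting because a stated rule gives the wrong label and the correction is cheap.

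**What to change.** In protocol 11.2.2.1 and on the adverse event form, record relationship to trial drug and relationship to trial procedure as two items. In protocol 13.3.2 and SAP 5.3.2, define adverse drug reactions and all related rows on the drug item only, and add one line for procedure-only events. Events of doubtful cause stay as adverse drug reactions.

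If data are already collected, ask the blinded investigator, for each event rated *Reasonable Possibility*, whether the drug or only a procedure was suspected. Do this before the code is broken, and preferably before database lock, since SAP 5.1.1 places the blind review after lock. Keep the original rating in the listing. Causality is the investigator's judgment, so it should not be reassigned at the data review.

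The cost is one extra item on the form or a few queries, plus small wording changes in the SAP.
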